11.3.7 HIE (Thompson score)

The Thompson score will be used to measure the severity of HIE for subjects with HIE at the timepoints described in [Table 5–1](#) and [Table 5–2](#) for the Exploratory and Confirmatory Cohorts, respectively.

The Thompson score is derived from 9 aspects of the neurological examination of infants with HIE: the total score ranges from 0 to 22 and the kappa coefficient is 0.87 (Thompson et al, 1997). This score allows a more precise description of infants than “mild”, “moderate” or “severe” and recognizes the prognostic significance of mixed signs within these 3 categories. In normothermic infants, a maximum score >10 during the first 7 days of life predicts an abnormal outcome with 100% sensitivity and 61% specificity (Thompson et al, 1997).

11.3.8 Withdrawal and rebound phenomena

Withdrawal and rebound phenomena will be assessed by observing any AEs experienced by subjects following the cessation of BRV administration. These AEs will be reported by the Investigators, and any AEs relating to BRV withdrawal will be used for the analysis of withdrawal and rebound phenomena. Withdrawal and rebound phenomena, if any, will be captured from data collected at the end of BRV exposure for subjects in both the Exploratory and Confirmatory Cohorts.

11.3.9 Mechanical ventilation

Numbers and percentage of subjects requiring mechanical ventilation will be recorded from Baseline through the 48-hour Evaluation Period for the Exploratory Cohort and the 96-hour Evaluation Period for the Confirmatory Cohort.

Duration of mechanical ventilation will be recorded over the Evaluation Period.

11.3.10 Bayley Scales of Infant and Toddler Development, Third Edition

The Bayley-III scales will be used in this study. The data collected will not be used for analysis, but as the Baseline for subjects who are entering the long-term study.

The Bayley-III scales are recognized internationally as one of the most comprehensive developmental assessment instruments (Sattler and Hoge, 2006) used to examine the major facets of a young child’s development (Bayley, 2006). The Bayley-III scales are a standardized, individually administered adaptive assessment that measures the developmental functioning of infants and young children from 1 month to 42 months of age (Bayley, 2006). The Bayley-III scales measure cognitive, language, motor, social-emotional, and adaptive.

The Bayley-III scales are an individually administered adaptive assessment that presents children with situations and tasks designed to produce an observable set of behavioral responses. They consist of a cognitive scale, a language composite scale with receptive and expressive language subscales, a motor composite scale with fine and gross motor subscales to be completed by the Investigator or designee, a social-emotional scale, comprising social-emotional competence, and sensory processing, and an adaptive behavior scale, which assesses the attainment of skills necessary for the development of independence, to be completed by the neonate’s parent(s) or caregiver.

The Bayley-III scales will be completed before the subject enters the long-term study (at EPV 2) and again in the long-term study for subjects enrolled in countries where a validated translation of the scale is available in the local language.

12 STUDY MANAGEMENT AND ADMINISTRATION

12.1 Adherence to protocol

The Investigator should not deviate from the protocol. However, the Investigator should take any measure necessary in deviation from or not defined by the protocol to protect clinical study subjects from any immediate hazard to their health and safety. In this case, this action should be taken immediately, without prior notification of the regulatory authority, IEC, or Sponsor.

After implementation of such a measure, the Investigator must notify the Clinical Project Manager of the Sponsor within 24 hours and follow any local regulatory requirements.

12.2 Monitoring

Monitoring of the study will be delegated by UCB to a CRO. The CRO will monitor the study to meet the CRO's monitoring Standard Operating Procedures (SOPs), ICH-GCP guideline, and applicable regulatory requirements, and to ensure that study initiation, conduct, and closure are adequate.

The Investigator and his/her staff are expected to cooperate with UCB (or designee) and to be available during the monitoring visits to answer questions sufficiently and to provide any missing information. The Investigator(s)/institution(s) will permit direct access to source data/documents for study-related monitoring, audits, IEC review, and regulatory inspection(s).

The Investigator will allow UCB (or designee) to periodically review the eCRF entries against the corresponding source documents (eg, hospital and laboratory records for each study participant). Monitoring visits will provide UCB (or designee) with the opportunity to evaluate the progress of the study, verify the accuracy and completeness of eCRFs, ensure that all protocol requirements, applicable authorities' regulations, and Investigator's obligations are being fulfilled, and resolve any inconsistencies in the study records.

12.2.1 Definition of source data

All source documents must be accurate, clear, unambiguous, permanent, and capable of being audited. They should be made using some permanent form of recording (ink, typing, printing, optical disc). They should not be obscured by correction fluid or have temporary attachments (such as removable self-stick notes). Printouts of eCRF screens are not considered acceptable source documents.

Source documents are original records in which raw data are first recorded. These may include hospital/clinic/general practitioner records, charts, diaries, x-rays, laboratory results, printouts, pharmacy records, care records or other printouts, completed scales, quality of life questionnaires, or video, for example. Source documents should be kept in a secure, limited access area.

Apart from the VEEG, other source documents that may be computer generated and stored electronically must be printed for review by the monitor. Once printed, these copies should be signed and dated by the Investigator and become a permanent part of the subject's source

documents. The Investigator will facilitate the process for enabling the monitor to compare the content of the printout and the data stored in the computer to ensure all data are consistent.

12.2.2 Source data verification

Source data verification ensures accuracy and credibility of the data obtained. During monitoring visits, reported data are reviewed with regard to being accurate, complete, and verifiable from source documents (eg, subject files, recordings from automated instruments, tracings [VEEG], laboratory notes). All data reported on the eCRF should be supported by source documents, unless otherwise specified in Section 12.2.1.

12.3 Data handling

12.3.1 Case Report form completion

The Investigator is responsible for prompt reporting of accurate, complete, and legible data in the eCRFs and in all required reports.

Any change or correction to the eCRF after saving must be accompanied by a reason for the change.

Corrections made after the Investigator's review and approval (by means of a password/electronic signature) will be reapproved by the Investigator.

The Investigator should maintain a list of personnel authorized to enter data into the electronic eCRF.

Detailed instructions will be provided in the eCRF Completion Guidelines.

12.3.2 Database entry and reconciliation

Case Report forms/external electronic data will be entered/loaded into a validated electronic database using a clinical data management system (CDMS). Computerized data cleaning checks will be used in addition to manual review to check for discrepancies and to ensure consistency of the data. This study will be performed using remote data capture. The data are entered into the eCRFs once and are subsequently verified if the study is performed using electronic data capture.

An electronic audit trail system will be maintained within the CDMS to track all data changes in the database once the data have been saved initially into the system or electronically loaded. Regular backups of the electronic data will be performed.

12.3.3 Subject Screening and Enrollment log/Subject Identification Code list

The subject's screening and enrollment will be recorded in the Subject Screening and Enrollment Log.

The Investigator will keep a Subject Identification Code list. This list remains with the Investigator and is used for unambiguous identification of each subject.

The subject's consent and enrollment in the study must be recorded in the subject's medical record. These data should identify the study and document the dates of the subject's participation.

12.4 Termination of the study

UCB reserves the right to temporarily suspend or prematurely discontinue this study either at a single site, multiple sites, or at all sites at any time for reasons including, but not limited to, safety or ethical issues, inaccurate or incomplete data recording, noncompliance, or unsatisfactory enrollment with respect to quality or quantity.

If the study is prematurely terminated or suspended, UCB (or its representative) will inform the Investigators/institutions and the regulatory authority(ies) of the termination or suspension and the reason(s) for the termination or suspension, in accordance with applicable regulatory requirement(s). The IEC should also be informed and provided with reason(s) for the termination or suspension by the Sponsor or by the Investigator/institution, as specified by the applicable regulatory requirement(s). In addition, arrangements will be made for the return of all unused BRV and other material in accordance with UCB procedures for the study.

12.5 Archiving and data retention

The Investigator will maintain adequate records for the study, including eCRFs, medical records, laboratory results, Informed Consent documents, drug dispensing and disposition records, safety reports, information regarding participants who discontinued, and other pertinent data.

All essential documents are to be retained by the Investigator until at least 2 years after the last approval of a marketing application in an ICH region and until there are no pending or contemplated marketing applications in an ICH region, or at least 2 years have elapsed since the formal discontinuation of clinical development of the IMP. These documents should be retained for a longer period, however, if required by the applicable regulatory requirement(s) or by an agreement with UCB (Committee for Proprietary Medicinal Products [CPMP]/ICH/135/95, 2002 [Section 4.9.5]). The Investigator will contact UCB for authorization prior to the destruction of any study records or in the event of accidental loss or destruction of any study records. The Investigator will also notify UCB should he/she relocate or move the study-related files to a location other than that specified in the Sponsor's trial master file.

12.6 Audit and inspection

The Investigator will permit study-related audits mandated by UCB, after reasonable notice, and inspections by domestic or foreign regulatory authorities.

The main purposes of an audit or inspection are to confirm that the rights and well-being of the subjects enrolled have been protected, that enrolled subjects (ie, signing consent and undergoing study procedures) are appropriate for the study, and that all data relevant for the evaluation of the IMP have been processed and reported in compliance with the planned arrangements, the protocol, investigational site, and IEC SOPs, ICH-GCP, and applicable regulatory requirements.

The Investigator will provide direct access to all study documents, source records, and source data. If an inspection by a regulatory authority is announced, the Investigator will immediately inform UCB (or designee).

12.7 Good Clinical Practice

Noncompliance with the protocol, ICH-GCP, or local regulatory requirements by the Investigator, institution, institution staff, or designees of the Sponsor will lead to prompt action

by UCB to secure compliance. Continued noncompliance may result in the termination of the site's involvement in the study.

13 STATISTICS

A description of statistical methods follows and will be given in more detail in the Statistical Analysis Plan (SAP). In general, descriptive summaries will be used to present the study results overall and by cohorts (Exploratory Cohort and each individual Confirmatory Cohort).

13.1 Definition of analysis sets

Analysis sets will be defined as follows:

- The Pharmacokinetic Per-Protocol Set will consist of all subjects who provide at least 1 measurable plasma sample (with recorded sampling time) on at least 1 post-Baseline visit with documented study drug intake times. This analysis set will be used for the Exploratory Cohort and the Confirmatory Cohort(s).
- The SS will consist of all enrolled subjects who take at least 1 dose of BRV. All safety analyses will be performed on the SS for the Exploratory Cohort and the Confirmatory Cohort(s).
- The Full Analysis Set will be used for the analysis of seizure data (efficacy) and will consist of all subjects in the SS who have a minimum of 2 hours of interpretable VEEG data from both the Baseline period and the first 3 hours of the post-Baseline period after initial BRV treatment.

13.2 General statistical considerations

Descriptive statistics, such as the mean, standard deviation, median, 25th percentile, 75th percentile, minimum value, and maximum value will be provided for quantitative variables. Counts and percentages will be provided for categorical variables. Confidence intervals (CIs) (95%) will be provided for efficacy variables, which will be described in the SAP. Key supporting data will be provided in data listings.

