6 SELECTION AND WITHDRAWAL OF SUBJECTS

6.1 Inclusion criteria

To be eligible to participate in this study, all of the following criteria must be met:

1. An Independent Ethics Committee (IEC)-approved written ICF is signed and dated by the parent(s) or legal representative(s).
- 2a. Confirmation on VEEG of ≥ 2 minutes of cumulative ENS or ≥ 3 identifiable ENS prior to entering the Evaluation Period (ENS is defined as a seizure lasting for at least 10 seconds on VEEG), despite receiving previous AED treatment for the treatment of electroencephalographic seizures.

The occurrence of ENS during an up to 1-hour period must be confirmed either by the local or central VEEG reader prior to drug administration. Preferably, the central VEEG reader should confirm the required ENS.

3. Subject is male or female and must be at least 34 weeks of CGA. In addition, term neonates up to 27 days of PNA and preterm neonates up to 40 weeks of CGA and 27 days of PNA can be enrolled.
4. Subject weighs at least 2.3kg at the time of enrollment.
5. Subjects with or without concomitant hypothermia treatment.

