- Percent reduction in average seizure burden measured by continuous VEEG from Baseline to the end of the 96-hour Evaluation Period
- Proportion of BRV responders at the end of the 96-hour Evaluation Period
- Proportion of subjects who are seizure-free (100% reduction in seizure burden from Baseline) at 24 hours following the start of initial BRV treatment, categorized by subjects with nonsevere or severe seizure burden at Baseline
- Time to reduction in seizure burden for BRV responders (defined as the first timepoint when BRV responder criteria are met)
- Seizure freedom at the end of the Down-Titration Period (Confirmatory Cohorts only)

- Rate of at least 50% reduction in ENS frequency per hour from Baseline to the end of the 96-hour Evaluation Period
- Proportion of subjects who are seizure-free by time interval at 3 hours, at 3-hour intervals thereafter through 24 hours, and every 12 hours to 24 hours following the start of the initial BRV treatment
- Absolute difference in clinical seizures at the end of the 24-hour Evaluation Period from Baseline for neonates with motor seizures at the time of inclusion
- Percent difference in clinical seizures at the end of the 24-hour Evaluation Period from Baseline for neonates with motor seizures at the time of inclusion

Historical controls will be matched by age and condition, using comparable standard of care and diagnostic methods. The efficacy of BRV will be evaluated for the main efficacy variable by comparing the 95% CI of the BRV responder rate (with all Confirmatory Cohorts combined) to responder rates for the referenced historical control group. If the BRV lower 95% CI limit is higher than the historical control group responder rate, then BRV would be considered efficacious compared to the historical control group. If the BRV upper 95% CI limit is lower than the historical control group responder rate, then BRV will not be considered efficacious compared to the historical control group. If the BRV 95% CI limits contain the historical control group responder rates, then the results will be considered inconclusive.

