3 DATA ANALYSIS CONSIDERATIONS

3.1 General presentation of summaries and analyses

Statistical analysis and generation of tables, figures, subject data listings, and statistical output will be carried out using SAS® Version 9.3 or higher.

Descriptive statistics, such as the number of subjects with available measurement (n), mean, standard deviation (SD), median, minimum value, and maximum value for quantitative variables, and counts and percentages for categorical variables, will be provided. Confidence intervals (95% CIs) will be provided for efficacy variables.

Unless otherwise noted, denominator for percentages will generally be based on the set of subjects with at least 1 assessment at the time point or at least 1 assessment during the time interval being summarized.

Decimal places for descriptive statistics will always apply the following rules:

- “n” will be an integer.
- Mean, SD and median will use 1 additional decimal place compared to the original data.
- Minimum and maximum will have the same number of decimal places as the original value.

Unless otherwise noted, all percentages will be displayed to 1 decimal place. No percentage will be displayed for zero counts, and no decimal will be presented when the percentage is 100%.

In general, descriptive summaries will be used to present study results overall (for the Confirmatory Cohorts) and by cohorts (Exploratory Cohort and each individual Confirmatory Cohort).

Subject data listings will be provided and will present source data and key derived variables for statistical analyses.

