8.2.5 Analysis of the secondary efficacy variables

Categorical secondary efficacy variables will be summarized using descriptive statistics (counts and proportions with the 95% CIs). Continuous key efficacy variables will be analyzed descriptively as described in [Section 3.1](#).

Time to reduction in seizure burden will be summarized descriptively by individual Confirmatory Cohorts and for all combined Confirmatory Cohorts, the cumulative number of events (response to BRV), Kaplan-Meier estimates at each hour during the Evaluation Period and median time to seizure burden reduction with 95% confidence interval will be provided. Also, graphical displays of Kaplan-Meier curves will be provided for each cohort separately.

A listing of secondary efficacy variables will be provided for the FAS.

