13 AMENDMENT(S) TO THE STATISTICAL ANALYSIS PLAN (SAP)

13.1 Change from Final SAP 26 April 2018 to SAP Amendment 1

- List of abbreviations was updated
- **Section 1:** updated protocol version
- **Section 2.1** and throughout the rest of the SAP: phenobarbital (PB) was replaced by previous antiepileptic drug (AED)
- **Section 2.2:** aligned the sub-sections to the protocol to stay consistent between the documents
- **Section 2.2.1:** added endpoint Plasma concentrations of BRV on other occasions
- **Section 2.2.2:**
 - separate section for main efficacy variable was removed to stay consistent between SAP and protocol
 - endpoints were listed and derivation of endpoints were removed from this section
- **Section 0:** section was aligned with protocol to define secondary safety variable (AE) and list other safety variables
- **Section 2.3:**
 - The sentence “N01349 consists of 2 steps including a comparison with a historical control from literature (midazolam (MDZ) treatment from literature of subjects matched in age and condition) for the evaluation of efficacy.” was replaced by “N01349 consists of a 2-step design and includes a descriptive comparison with a historical control group (matched in age and condition) from literature treated with AEDs per System Organ Class (SOC) and diagnostic methods.”
 - “multiple therapeutic doses of MDZ” was replaced by “AEDs for the treatment of ENS per SOC (first-line, second-line, or subsequent treatment; choice of treatment “.
 - Reference “N01266” as long term study was removed to use a more general wording
- **Section 2.3.1** and **Section 2.3.2** : Specified information about study periods and cohorts, and reworded for clarification according to protocol amendments.
- **Section 2.3.3:** Specified periods for the Confirmatory Cohorts
- **Section 2.4:**
 - Removed “MZD treated”
 - Specified that only subject from Confirmatory Cohort who drop out or withdrawal will not be replaced.
- **Section 3.1:** 25th and 75th percentile were removed from standard descriptive statistics as there are not foreseen in the standard mock shells.
- **Section 3.2.1.2:** Corrected typo of “mediation” to “medication”

- **Section 3.2.2:** Removed all repeated texts from **Section 2.3** and defined start and end of each study period for Exploratory Cohort and Confirmatory Cohorts.
- **Section 3.2.4:** Section added to describe who is classified as completing the study.

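### For percent reduction in seizure burden, SAP 3.1 drops the quartiles listed in Protocol 13.2 and does not say what its 95% CI estimates; one baby with a small Baseline can dominate the mean (minor, free to fix)

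*Protocol*

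**What the plan says.** Protocol 13.2 gives the summaries for quantitative data: "mean, standard deviation, median, 25th percentile, 75th percentile, minimum value, and maximum value will be provided for quantitative variables". It adds that 95% CIs will be given for efficacy variables and leaves their description to the SAP.

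SAP 3.1 lists "mean, standard deviation (SD), median, minimum value, and maximum value for quantitative variables", together with n, and states that "Confidence intervals (95% CIs) will be provided for efficacy variables". The quartiles are gone. SAP 13.1 gives the reason: "25th and 75th percentile were removed from standard descriptive statistics as there are not foreseen in the standard mock shells". SAP 3.10 (Table 3.1), which is meant to hold changes to protocol-defined analyses, has one entry, on the seizure-cause subgroups.

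For the secondary variables, SAP 8.2.5 says "Continuous key efficacy variables will be analyzed descriptively as described in" SAP 3.1, and SAP 8.3.2 does the same for the other efficacy variables. One secondary variable is "Percent reduction in average seizure burden measured by continuous VEEG from Baseline to the end of the 96-hour Evaluation Period". Percent reduction in eight time intervals is among the other variables. A CI for a median is named only for time to reduction in seizure burden.

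**The concern.** Percent reduction is a ratio with Baseline in the denominator. It has a hard ceiling at 100% improvement, and its floor depends on how small Baseline is. For such a variable the mean, the SD and any CI built on them can be set by the baby with the smallest Baseline rather than by the typical baby. The quartiles would show the spread of the bulk of the data, and they were removed for a layout reason, not a statistical one.

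The CI is a separate gap. The protocol defers its description to the SAP, and the SAP gives neither the parameter nor the method for continuous efficacy variables. The choice then falls to programming or to the report. In an open-label, single-arm study it is better made before the data are seen.

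**Working it through.** **Inputs**
- Percent reduction = 100 x (B - P)/B, with B the Baseline and P the post-dose burden in min/h (SAP 8.1.5).
- Smallest eligible Baseline: entry needs "≥ 2 minutes of cumulative ENS or ≥ 3 identifiable ENS prior to entering the Evaluation Period", and each ENS lasts at least 10 seconds. Three at 10 s in one hour give 3 x 10/60 = 0.5 min/h. The cumulative route gives 2 min/h.
- P lies between 0 and 60 min/h by definition.
- At least 36 Confirmatory subjects, in cohorts of 12.

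The documents give no range, power or precision figure for this variable, so there is none to reproduce.

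**Range**
- Ceiling: P = 0 gives +100%.
- Floor at B = 0.5: 100 x (0.5 - 60)/0.5 = -11,900%.
- Floor at B = 2: 100 x (2 - 60)/2 = -2,900%.
- Floor at B = 30: 100 x (30 - 60)/30 = -100%.

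The floors need uninterrupted seizure over the whole interval, so they are limits, not expected values.

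**One outlying baby.** Assumption: every other baby has an 80% reduction. The outlier goes from 0.5 to 10 min/h: 100 x (0.5 - 10)/0.5 = -1,900%.

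n = 36:
- Mean = (35 x 80 - 1,900)/36 = 900/36 = 25%.
- SD = sqrt[(35 x 55² + 1,925²)/35] = sqrt(108,900) = 330.
- 95% t-interval = 25 ± 2.030 x 330/6 = 25 ± 111.7, or -87% to +137%. The upper limit lies above the 100% ceiling.
- Median, Q1 and Q3 are all 80%.

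n = 12:
- Mean = (11 x 80 - 1,900)/12 = -85%.
- SD = sqrt[(11 x 165² + 1,815²)/11] = 571.6.
- 95% t-interval = -85 ± 2.201 x 165.0, or -448% to +278%.
- The median is again 80%.

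**What it takes to change the sign of the mean.** One value must fall below -(n - 1) x 80%.

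| n | Value needed | P if B = 0.5 | P if B = 2 |
|---|---|---|---|
| 36 | below -2,800% | above 14.5 min/h | above 58 min/h |
| 12 | below -880% | above 4.9 min/h | above 19.6 min/h |

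**Effect of restoring the quartiles alone.** The mean, SD and CI do not change. Q1 and Q3 add a view of spread beside the median already planned.

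**Order-statistic CI for the median.** For n = 36 the 12th and 25th ordered values give coverage 1 - 2 x P(X ≤ 11) = 97.1%, with X binomial(36, 0.5). For n = 12 the 3rd and 10th give 1 - 2 x P(X ≤ 2) = 96.1%. Both exist at the planned sizes.

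**Sign convention.** SAP 8.2.4 defines the 96-hour absolute reduction as post minus Baseline and divides it by Baseline for the percentage. SAP 8.1.5 and 8.3.1 use Baseline minus post. The same 80% improvement is therefore -80% as the 96-hour secondary variable and +80% in the interval and categorised variables. The ranges above follow SAP 8.1.5; under SAP 8.2.4 the signs reverse.

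**The case against.** A reader might infer that dropping the quartiles lets one baby reverse the reported effect. The documents do not support that, for four reasons.

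- The sensitivity belongs to the mean, which Protocol 13.2 lists too.
- SAP 3.1 keeps the median, minimum and maximum, and the median does not move in any of the examples.
- SAP 8 limits efficacy interpretation to the combined Confirmatory Cohorts. There the worked example gives +25%, which is diluted but not reversed. The negative mean appears only at n = 12.
- A CI for the mean is an inference. SAP 8.2.5 and 8.3.2 attach CIs expressly to categorical variables, and SAP 3.1 names no parameter for continuous ones.

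A reader might also infer a concealed breach of a protocol requirement. Protocol 13.2 introduces its list as examples, and SAP 13.1 records the removal with a reason. The gap is only that Table 3.1 omits it.

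Other protections are real. The main secondary variable is a responder proportion, percent reduction is also reported in five bands with one for worsening, individual listings are planned, and all analyses are descriptive with no tests. The optional log(x + 1) transformation is weaker protection, because no condition triggers it.

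What stands is that the quartiles differ between the two documents, the CI is undefined for continuous variables, and no lead summary is named for a heavily skewed one.

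**Conclusion.** The point holds as a minor specification gap. The mean, SD and any CI for the mean of percent reduction can be dominated by one baby with a small Baseline: 25% (-87% to +137%) at n = 36, against a median of 80%. This rests on an assumed pattern, with 35 identical responders and one outlier. How often such an outlier would occur cannot be learned from the documents. In simulations with a true median reduction of 70% and n = 36, Baseline was assumed log-uniform on 0.5 to 30 min/h and the post/Baseline ratio lognormal. The mean was then negative in about 0.1% of trials at a log-SD of 1.0, 22% at 1.5 and 71% at 2.0. No document supports any of these spreads, so that range shows dependence on the assumption and is not a forecast.

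The trial's main efficacy conclusion is not at risk, because it rests on a proportion. The gain is a continuous summary that describes the typical baby and an interval fixed in advance.

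**What to change.** 1. SAP 3.1: restore the 25th and 75th percentiles, or declare their removal in Table 3.1.
2. SAP 8.2.5 and 8.3.2: for percent reduction in seizure burden and percent difference in clinical seizures, name median (Q1, Q3) with an order-statistic 95% CI for the median as the summary to interpret. Keep mean and SD as extra rows without a CI.
3. SAP 8.2.4: define the 96-hour absolute and percent reduction as Baseline minus post, to match SAP 8.1.5 and 8.3.1.

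The cost is SAP wording and a few rows in the table shells, settled before database lock. It needs no extra data or patients, and nothing now planned is lost except a CI for the mean, if one was intended for these variables. In the simulations the median interval covered the true value in about 97% of trials and was 17%, 45% and 62% narrower than the interval for the mean at the three assumed spreads.
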